HEOR	Health Economics, Outcomes & Reimbursement
IBW	Ideal Body Weight
ICH	International Committee on Harmonization
ID	Identifier
INN	International Non-proprietary Name
ITT	Intent-to-treat
IV	Intravenous

IVRS/IWRS	Interactive voice/web response system
IXRS	Interactive response system (independent of type)
JSRC	Joint Safety Review Committee
kBq	Kilobecquerel
LCL	Lower Confidence Limit
LTFU	Long-Term Follow-Up
LTFUAE	Long-Term Follow-Up Adverse Event
MedDRA	Medical Dictionary for Regulatory Activities
MRI	Magnetic resonance imaging
NCI	National Cancer Institute
NCCN	National Comprehensive Cancer Network
NIS	Non-interventional Study
NIST	National Institute of Standards and Technology
nMiss	Number of missing values
OS	Overall survival
PC	Prostate cancer
mPCWG2	Modified Prostate Cancer Working Group 2
PRO	Patient Reported Outcomes
PSA	Prostate specific antigen
PT	Preferred Term
QoL	Quality of Life
Ra-223	Radium-223 dichloride
rPFS	Radiological progression free survival
SAE	Serious Adverse Event
SAF	Safety
SAP	Statistical Analysis Plan
SD	Standard Deviation
SMQ	Standardized MedDRA Queries
SOC	System Organ Class
SOP	Standard Operating Procedure
SSE	Symptomatic skeletal event
SSE-FS	Symptomatic skeletal event free survival
Std	Standard Deviation
TAS	(Bayer) Therapeutic Area (Oncology) Standards
TBW	Total Body Weight
TEAE	Treatment-Emergent Adverse Event
TTP	Time to progression
uCi	Microcurie
UCL	Upper Confidence Limit
W12	Week 12
W24	Week 24
WHO	World Health Organization
WHO-DD	World Health Organization Drug Dictionary

1. Introduction

Protocol 16507 is a 3-arm, randomized, open-label Phase II study to compare the efficacy and safety of a “standard dose” regimen of radium-223 dichloride with, a “high dose” regimen and an “extended dose” regimen, in subjects with castration-resistant prostate cancer metastatic to bone .

The study's 3 arms are:

- Arm A: 6 doses of 50 kBq/kg (55 kBq/kg after implementation of NIST update) radium-223 dichloride every 4 weeks ("standard" dose regimen)
- Arm B: 6 doses of 80 kBq/kg (88 kBq/kg after implementation of NIST update) radium-223 dichloride every 4 weeks ("high dose" regimen)
- Arm C: 12 doses of 50 kBq/kg (55 kBq/kg after implementation of NIST update) radium-223 dichloride every 4 weeks ("extended dose" regimen)

The study's co-primary endpoints are:

- Symptomatic skeletal event free survival from randomization (SSE-FS1) for the "standard dose" vs. "high dose" comparison (Comparison 1).

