6.4.1 Adverse events

All adverse events (AE) will be coded according to the latest Medical Dictionary for Regulatory Activities (MedDRA) Version as of database lock for the applicable analysis. The MedDRA version used will be documented in the CSR. The intensity of an AE will be documented using the NCI-CTCAE v4.03.

Adverse Events of Interest

A summary table and a listing will be provided for subjects who experienced following adverse events: pancytopenia and myelotoxicity including myelodysplastic syndrome, aplastic anemia and myelofibrosis. The events will be identified by medical reviewer based on verbatim recorded in database.

Treatment Period Analyses

The treatment period for this study, for purposes of safety analyses, extends from the initiation of study treatment until 30 days after the last administration of radium-223 dichloride.

Pre-treatment AEs

Pre-treatment AEs will be defined as AEs that started and either stopped before the first dose of study treatment or continued after and did not worsen in intensity (i.e. increase in CTCAE toxicity grade or became serious) during the treatment period.

Treatment-emergent AEs

All AEs starting or worsening within the treatment period will be considered TEAEs,

Post-treatment AEs

Post-treatment follow-up AEs will be defined as AEs that started after the treatment period. Note that the intention of this study is that only treatment-related AEs will be collected after the treatment period.

An overall summary of AEs will be provided to present the number and percentage of subjects with

- any pre-treatment AEs TEAEs, or post-treatment AEs
- any study treatment related TEAEs
- any serious TEAEs,
- any serious treatment related TEAEs
- any CTCAE Grade ≥ 3 TEAEs
- any TEAEs leading to drug modification or discontinuation
- any TEAEs leading to death
- any AEs leading to drug modification or discontinuation

TEAEs and post-treatment AEs will be summarized by MedDRA system organ class and preferred term. For each subject, multiple occurrences of the same event will be counted once within a system organ class and preferred term. For post-standard treatment AE tables, only treatment-related AEs, serious treatment-related AEs will be reported. Subjects who received 6 or less doses from Arm A and C versus subjects received 7 or more doses in Arm C will also be summarized for evaluating potential cumulative toxicity of extended regimen.

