The same summaries will be repeated for related TEAEs, serious TEAEs, serious related TEAEs, CTCAE Grade ≥ 3 TEAEs, TEAEs leading to drug modification or discontinuation, TEAEs leading to death and any AEs leading to drug modification or discontinuation.

The maximum severity of the TEAEs and post-treatment AEs will be summarized according to the NCI-CTCAE toxicity criteria. For each subject, multiple occurrences of the same event will be counted once at their maximum severity within a system organ class and preferred term. TEAE will also be summarized by NCI-CTCAE toxicity criteria and relationship to study medication.

The numbers of subjects experiencing TEAEs will be presented.

The analysis of TEAEs will be reported by treatment group as treated (Arm A, Arm B, and Arm C).

Long-Term Follow-Up AEs

Long-term follow-up AEs are AEs arising during the long-term follow-up period. LTFU AEs will not be included in safety analysis summary tables for this study, but will be included in listings.

AE Listings

Data listings will be produced for all AE recorded in the study. Verbatim descriptions and coded terms will be listed for all AEs.

Serious adverse events (SAEs), deaths, AEs leading to discontinuation and AEs of interest will each have a separate listing.

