If more than one assessment occurred at any visit (i.e. repeat samples taken), the last valid (non-missing) value will be used in the summaries. Unscheduled laboratory data will not be included in the by visit summary tables, however will be included in the overall CTCAE grade tables.

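### TEAE percentages are compared crudely across arms, although the planned TEAE window is about 24 weeks in Arms A and B and about 48 weeks in Arm C

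*SAP*

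**What the plan says.** SAP Section 1 sets the regimens:

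- "Arm A: 6 doses of 50 kBq/kg (55 kBq/kg after implementation of NIST update) radium-223 dichloride every 4 weeks"
- "Arm B: 6 doses of 80 kBq/kg (88 kBq/kg after implementation of NIST update) radium-223 dichloride every 4 weeks"
- "Arm C: 12 doses of 50 kBq/kg (55 kBq/kg after implementation of NIST update) radium-223 dichloride every 4 weeks"

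Section 6.4.1 defines the treatment period for safety as one that "extends from the initiation of study treatment until 30 days after the last administration of radium-223 dichloride". An AE that starts or worsens in that period is a TEAE. Beyond it, the stated intention is that "only treatment-related AEs will be collected after the treatment period".

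The summary measure is a crude count: "An overall summary of AEs will be provided to present the number and percentage of subjects with" each category of event. In the tables by system organ class and preferred term a subject counts once per term. The grouping is fixed by "The analysis of TEAEs will be reported by treatment group as treated (Arm A, Arm B, and Arm C".

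The same section adds a summary for cumulative toxicity. It sets subjects from Arms A and C with six or fewer doses against Arm C subjects with seven or more. The main SAP specifies no exposure-adjusted rate, time-to-event summary or common-window summary for TEAEs. Version 2.0 of the supplement (Section 6.5.1) adds Kaplan-Meier summaries by arm for time to fracture only.

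For laboratory data, Section 6.4.3 leaves unscheduled values out of the by-visit tables, but they "however will be included in the overall CTCAE grade tables". No time window is given for those overall tables.

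**The concern.** Crude percentages compare arms fairly only when subjects are observed for similar lengths of time. Here the observation time is set by the regimen. An unrelated infection or fracture in Week 36 is a TEAE in an Arm C subject who is still being dosed. In an Arm A subject who finished six doses it is not meant to be collected at all. Arm C can therefore show a higher percentage with no difference in risk per unit of time.

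Safety and tolerability is the first secondary objective in Section 2, and these arm-level tables are where the extended regimen will be read against the standard one. The SAP deals with the same lack of comparability on the efficacy side: Section 4.5.2 cuts Arm C off at the 7th dose when it is pooled with Arm A. Safety has no counterpart.

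**Working it through.** **Planned windows.** With k doses every 28 days the window is 28(k − 1) + 30 days.

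- Arms A and B, k = 6: 140 + 30 = 170 days = 24.3 weeks.
- Arm C, k = 12: 308 + 30 = 338 days = 48.3 weeks.
- Ratio: 338/170 = 1.99.

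**The plan's own attrition figure, reproduced.** The SAP gives no numerical assumption for safety. The figure that bears on how many Arm C subjects reach the longer window is in Section 3.4: 55.35% of Arms A and C (132.8 of 240) event-free and still followed at 24 weeks. The inputs are a median SSE-FS of 9 months and 3% loss per month.

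- Monthly hazard: ln 2/9 + (−ln 0.97) = 0.0770 + 0.0305 = 0.1075.
- 24 weeks = 168/30.4375 = 5.52 months.
- exp(−0.1075 × 5.52) = 0.553, or 132.6 of 240. With a loss hazard of 0.03 it is 0.554, or 132.9 of 240. The stated figure is reproduced.

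**Windows under that attrition.** Assumption: an SSE-FS event or loss to follow-up ends dosing. The SAP does not say so. Arm A keeps the hazard above. Arm C changes at Week 24 to ln 2/14.85 + 0.0305 = 0.0467 + 0.0305 = 0.0771 per month.

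- Mean doses: 4.75 in Arm A and 7.55 in Arm C.
- Mean window, Arm A: 28 × 3.75 + 30 = 135 days = 19.3 weeks.
- Mean window, Arm C: 28 × 6.55 + 30 = 213 days = 30.5 weeks.
- Ratio: 1.58. It is 1.54 if Arm C has no benefit after Week 24, and 1.69 if everyone who reaches dose 7 completes.

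**Effect on percentages.** Take one constant event rate λ in both arms. The expected percentage is the sum over k of P(k doses) × (1 − exp(−λ × window)). With complete dosing this reduces to Arm C = 1 − (1 − p)^1.99, where p is the Arm A percentage; for p = 10%, 1 − 0.90^1.99 = 18.9%. In the other columns λ is solved to give the stated Arm A percentage.

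| Arm A | Arm C, all complete (ratio) | Arm C, half the Section 3.4 hazards (ratio) | Arm C, full Section 3.4 hazards (ratio) |
|---|---|---|---|
| 5% | 9.7% (1.94) | 8.6% (1.72) | 7.7% (1.54) |
| 10% | 18.9% (1.89) | 16.7% (1.67) | 15.1% (1.51) |
| 30% | 50.8% (1.69) | 45.1% (1.50) | 40.9% (1.36) |
| 50% | 74.8% (1.50) | 66.9% (1.34) | 61.4% (1.23) |
| 70% | 90.9% (1.30) | 82.6% (1.18) | 77.3% (1.10) |

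**Does the dose-count summary repair it?** Under the full Section 3.4 hazards and the same equal rate, the group with six or fewer doses has a mean window of 17.4 weeks and the group with seven or more has 44.5 weeks, a ratio of 2.56. An event seen in 5% of Arm A would appear as 4.5% against 11.2%, about 2.5-fold. Membership depends on a dose count known only after baseline, and a subject has to stay on treatment to reach seven.

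**Does a rate per time at risk repair it?** Expected time to first event or end of window is (1 − exp(−λT))/λ. Dividing the expected number of subjects with an event, 1 − exp(−λT), by that time returns λ whatever T is. The Arm C to Arm A ratio is then 1.00 under equal constant rates.

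**The case against.** The tables are descriptive: Section 6.4 plans no formal safety tests. Crude incidence over each regimen as given is a legitimate account of the burden of a longer course. Section 6.1.4 reports treatment duration, number of injections and dose intensity by group, so a reader can see that exposure differs. Arms A and B have equal planned windows, so that contrast does not have this built-in imbalance. Rates per patient-year carry a constant-hazard assumption of their own. All of this stands, and it is why the planned tables should stay. But the exposure summaries sit beside the event percentages without adjusting them, and a descriptive table is still read as a comparison.

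A reader might go further and infer that Arm C will look about twice as toxic for any event with a constant rate. The documents do not support that. A factor near 2 needs both a rare event and near-complete dosing. The ratio falls as the event becomes more common, and Section 3.4 itself expects only about 55% of Arms A and C to be event-free and in follow-up at Week 24.

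A reader might also carry the 24 against 48 weeks over to the laboratory grade tables. That is not supported either. Section 6.4.3 does not tie the overall grade tables to the treatment period, and Section 3.2 leaves the schedule of procedures to the protocol. The telephone contacts described under BPI Subscales in Section 6.2.3 concern questionnaire completion, not blood sampling. By-visit summaries and box plots over time already allow same-visit laboratory comparisons across arms. What remains is that the overall grade tables have no stated window.

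**Conclusion.** The concern holds for TEAEs. Arm-level percentages are taken over windows that differ by design, with all-cause collection meant to stop when the window closes, and no planned output adjusts for it. Under equal constant rates Arm C is inflated relative to Arm A in every scenario tabulated. With complete dosing the factor is about 1.9 for events seen in 5% to 10% of Arm A and 1.3 at 70%. Over the same 5% to 70% range it is about 1.5 down to 1.1 if the Section 3.4 hazards are assumed to end dosing.

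These sizes rest on constant, equal event rates, doses given on schedule, and the attrition assumption, for which the complete-dosing case and the full Section 3.4 hazards mark the range shown. They do not predict the observed data, and they do not mean that any Arm C excess would be an artefact. For the laboratory tables only the missing window is established. This is a gap with a known direction and a cheap remedy. It does not invalidate the safety plan.

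**What to change.** In Section 6.4.1, keep the planned tables and add, by arm, subjects with TEAEs per patient-year at risk. Time at risk runs from first dose to the first event of that type or the end of the TEAE window. Do this at least for the overall, Grade 3 or higher and serious TEAE tables and for the main preferred terms.

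Optionally, show Arm C separately before and from the 7th dose. A note should say what each part can show. The earlier part compares Arms A and C under identical treatment, so it cannot measure toxicity of the additional doses. The later part has no concurrent all-cause comparator, because unrelated events are not meant to be collected in Arm A by then.

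In Section 6.4.3, state the time window of the overall CTCAE grade tables and use the same one for each arm.

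Dose dates and AE onset dates are enough, so no new data are needed. The cost is more output, and the rates assume a roughly constant hazard, which a footnote should say.

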6.4.2 Deaths

Deaths reported during the study period will be tabulated by treatment group.

6.4.3 Clinical Laboratory Data

The following laboratory parameters will be summarized:

- Complete blood count (CBC), including hematocrit, hemoglobin, red blood cell (RBC) count, mean corpuscular volume (MCV), mean corpuscular hemoglobin (MCH), mean corpuscular hemoglobin concentration (MCHC), white blood cell (WBC) count, platelet count, and differential blood count reported as absolute count or percentage for neutrophils, lymphocytes, monocytes, eosinophils, and basophils
- Chemistry panel, including serum creatinine, sodium, potassium, chloride, calcium, phosphorous, magnesium, total bilirubin, total ALP, AST, ALT, lactate dehydrogenase (LDH) (screening only), and albumin (screening only)
- Other parameters: PSA, serum testosterone

Hematological and biochemical laboratory values will be graded based on NCI CTCAE version 4.03. CTCAE severity grading for laboratory abnormalities are based on applicable laboratory threshold values outlined in NCI CTCAE v4.03. It should be noted that in the process of assigning toxicity grades of those lab parameters for which additional clinical information potentially can also influence the toxicity grade, this clinical information is in general not available and only the lab measurements are used for toxicity grading.

Hematological and biochemical laboratory toxicities assigned by the investigator that include clinical assessments are available in Adverse Events database and are summarized in Adverse Event tables.

Any additional specific handling of the CTCAE v4.03 toxicity grading assignments will be noted in the footnotes of the corresponding tables.

Laboratory parameters will be evaluated for subjects in the safety (SAF) population by treatment group (Arm A, B, C).

For each analysis, descriptive statistics (number of observations, mean, standard deviation, minimum, median and maximum values) will be presented for clinical laboratory tests (hematology and clinical biochemistry), their change from baseline by group. Box plots will be generated for hematology parameters over all visits, by group, to investigate trends over time and outliers in the data. Graphs of hematological toxicity parameters (boxplots of mean and quartile values over time) will be produced. Similar graphs of chemistry and/or other lab parameters may also be produced.

In addition, for each analysis, change from baseline will be summarized in shift tables according to CTCAE grade.

If more than one assessment occurred at any visit (i.e. repeat samples taken), the last valid (non-missing) value will be used in the summaries. Unscheduled laboratory data will not be included in the by visit summary tables, however will be included in the overall CTCAE grade tables.

6.4.4 New Primary Malignancies

The new primary malignancies will be summarized overall and by cancer type (n, percent), and reported through listings.

6.5 Analysis of Other Endpoints

6.5.1 ECOG Performance Status

For ITT subjects, the number and percentage of subjects in each category will be presented by treatment group. Changes from randomization baseline in PS on the ECOG scale will be summarized in shift tables by treatment group.

6.5.2 Quality of Life

Summaries of NCCN-FACT FPSI-17 questionnaire data will be performed for the ITT population and will be based on an as “observed” basis (i.e. no imputation for missing data performed) unless otherwise specified. Analyses of NCCN-FACT data are described in the sections on efficacy and exploratory endpoints.

6.5.3 Long Term Safety

Safety data arising during the long-term safety follow-up period in this study will be presented through listings. In the event subjects in this study transfer into a long term safety follow-up study for all or a portion of their long-term follow-up period, any data not collected in this study is outside the scope of this SAP.

6.6 Examination of Subgroups

Subgroup analyses will be conducted for the primary efficacy endpoint SSE-FS following randomization based on the ITT population, and SSE-FS following Week 24 baseline on the W24 population, and for secondary endpoint OS. Subgroup analyses will be provided by subgroup within each respective pooled treatment grouping, as described for the primary analysis for each comparison. Descriptive statistics and hazard ratio estimates with 80% and 95% CIs will be provided at least for the subgroups listed below, provided there is a sufficient number of events (at least 10 events) in total within the subgroup across the applicable pooled treatment groups. Hazard ratios by subgroup with 80% and 95% CIs will be plotted using forest plots.

- ECOG performance status at baseline (0 vs 1)
- Extent of Disease (number of bone lesions: <6, 6-20, >20 or superscan at baseline)
- Race (White, Asian and Other)
- Age group (<65, 65-74, 75-84, >=85 years)
- Baseline Total Body Weight and Ideal Body Weight normalized dose quartiles
- Randomization stratification factors:

- use of prior chemotherapy (≤ 1 regimen versus > 1 regimen)
- total ALP (< 220 U/L versus ≥ 220 U/L)
- average worst pain score (WPS) of the BPI-SF at screening assessment (WPS ≤ 4 versus WPS > 4).
- BMI
 - Low, non-low (< 18.5 and ≥ 18.5)
 - Non-high, high (< 30 and ≥ 30)
- Gleason Score at the time of diagnosis (< 8 , ≥ 8 , Missing)
- Baseline PSA values by median ($< \text{median}$, $\geq \text{median}$)
- Received prior anti-androgens at baseline: abiraterone or enzalutamide (Yes vs. No)

For time-to-event endpoints, Kaplan-Meier [5] estimates will be presented with median, 25th, and 75th percentile survival time and associated 80% and 95% Brookmeyer-Crowley [6] confidence intervals (CI), and number and percentage of censored observations.

Corresponding Kaplan-Meier curves will also be plotted. A Cox proportional hazards model will be fitted for each time-to-event secondary efficacy endpoint, with baseline BMI category coded as a binary covariate (low versus non-low).

Safety analysis (i.e. AE) will be conducted based on age subgroup, and ideal body weight normalized dose quartiles.

7. Document history and changes in the planned statistical analysis

- SAP 21 February 2016 version 1.0
- SAP 17 May 2017 version 2.0

Table 7–1 The Changes Between SAP V1.0 and SAP V2.0

Endpoints/Definitions	SAP V1.0	SAP V2.0
Week 24 baseline	The Week 24 baseline assessment was defined as the assessment within the window (Day 127, Day 211) (Week 24 target – 14 through Day 28 target + 14) closest to Day 169 (Week 24 target date), selecting the earlier date in the event of a tie.	‘Week 24 baseline’ is defined as the last non-missing value on or before the date of the 6 th injection for Arm A and Arm C.
Time to radiologic progression / rPFS/Bone scan time point & overall response	All imaging-based endpoints will be based on week-24 baseline for Comparison 2.	All imaging endpoints will be based on randomization baseline for Comparison 2.
PSA progression	Prostate specific antigen progression is defined with respect to each applicable baseline, as a $\geq 25\%$ increase	Will use the definition consistent with compound standard: Prostate specific antigen progression is defined as $\geq 25\%$ increase from the baseline value and an

	above the applicable nadir (lowest baseline or post-baseline) value, and an increase in absolute value of ≥ 2 ng/mL above the nadir.	increase in absolute value of ≥ 2 ng/mL, at least 12 weeks from baseline in subjects with no PSA decline from baseline; or $\geq 25\%$ increase and an absolute increase of ≥ 2 ng/mL above the nadir value, which is confirmed by a second consecutive value obtained 3 or more weeks later but within 9 weeks in subjects with an initial PSA decline from baseline.
Total ALP progression	Total ALP progression is defined with respect to each applicable baseline, as a $\geq 25\%$ increase above the applicable nadir (lowest respective baseline or post-baseline) value.	Will use the definition consistent with the compound standard: Alkaline phosphatase progression is defined as $\geq 25\%$ increase from the baseline value, at least 12 weeks from baseline in subjects with no ALP decline from baseline; or $\geq 25\%$ increase above the nadir value, which is confirmed by a second consecutive value obtained 3 or more weeks later but within 9 weeks in subjects with an initial ALP decline from baseline.
ALP response	Total ALP response is defined with respect to each applicable baseline, as a $\geq 30\%$ reduction of the blood total-ALP level compared to the baseline value.	Will use the definition consistent with the compound standard: Alkaline phosphatase response is defined as $\geq 30\%$ reduction of the blood level, compared to the baseline value, confirmed by a second consecutive ALP value 4 or more weeks later but within 9 weeks.
Increase in analgesic use algorithm	Use AQA score in the algorithm	Will be based on strength and type of analgesic use. No AQA score will be calculated.
Exploratory endpoint analyses	Both randomization baseline and week 24 baseline will be used in the analyses	Only randomization baseline will be used. Endpoints with respect to Week 24 baseline will not be derived as formal statistical comparisons will not be made.

8. References

1. Fine, D. Consequences of delayed treatment effects on analysis of time-to-event endpoints. *Drug Inform J.* 41:535–539 (2007)
2. Zhang, D., and Quan, H. Power and sample size calculation for log-rank test with a time lag in treatment effect. *Stat Med.* 28: 864–879 (2009)
3. Green B. and Duffull S. What is the best size descriptor to use for pharmacokinetic studies in the obese? *J Clin Pharmacol.* Aug 2004; 58(2): 119–133.
4. World Health Organization. “Obesity: Preventing and Managing the Global Epidemic. Report of a WHO Consultation.” *WHO Technical Report Series* 894. Geneva: WHO; 2000. 8-9.

5. Kaplan E and Meier P. Nonparametric estimation from incomplete observations. *J Amer Statist Assn* 53:457–481 (1958)
6. Brookmeyer R and Crowley J. A confidence interval for the median survival time. *Biometrics* 38:29-41 (1982)
7. Clopper C and Pearson E. The use of confidence or fiducial limits illustrated in the case of the binomial. *Biometrika* 26:404–413. (1934)
8. Brown M, et al. Computer-aided quantitative bone scan assessment of prostate cancer treatment response, *Nucl Med Commun.* 33:384-94 (2012)
9. National Comprehensive Cancer Network. *NCCN Clinical Practice Guidelines in Oncology: Adult Cancer Pain.* Version 2.2014.
12. <http://www.facit.org/FACITOrg/Questionnaires>.

9. Appendices

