6.1.4 Extent of Exposure

Extent of exposure will be summarized for the Safety population by treatment group, using descriptive statistics.

- Duration of study treatment will be calculated in days as the date of the last dose of study – date of the first dose of study treatment + 1
- Number of radium-223 dichloride injections received. Summary statistics will include both descriptive statistics of number of doses received, and number and percent of subjects by number of doses received
- Total activity of radium-223 dichloride (sum of activity in all doses) in kBq and kBq/kg
- Dose intensity of radium-223 dichloride calculated as total activity of radium-223 dichloride/(duration of study treatment + 27), in kBq/day and KBq/kg/day
- Number and percent of subjects with dose modifications (none, at least one interruption/delay)
- Normalized dose for total body weight (TBW) and ideal body weight (IBW) will be summarized by quartile:

Total body weight normalized dose=Activity in the first dose administered to subject /body weight used for first dose

Ideal body weight normalized dose= Activity in the first dose administered to subject /ideal body weight

All exposure summaries will be based on the old standard (50 or 80 kBq/kg). Hence, doses administered with the new standard (55 or 88 kBq/kg) will be converted to the old standard prior to any analyses as specified below. A country specific 2016 NIST implementation date will be utilized for this conversion.

Radioactivity will be calculated as follows:

- Activity per injection (kBq) = Activity in syringe before injection (kBq) - activity in syringe after injection (kBq)
- Activity adjusted
 1. If the dose date is prior to 2016 global NIST implementation date in the country, then Activity per injection = Activity per injection

2. If the dose date is after the 2016 global NIST implementation date in the country, then Activity per injection = Activity per injection/1.1

- Total activity injected (kBq) = Sum of ('Activity per injection')

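### In Comparison 1 the normalized-dose quartile subgroups are built from a variable that contains the randomised dose, so most of their hazard ratios are absent, or imprecise and confounded

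*SAP*

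**What the plan says.** SAP Section 6.6 lists "Baseline Total Body Weight and Ideal Body Weight normalized dose quartiles" among the subgroups for SSE-FS and OS. Each subgroup is to have descriptive statistics, a hazard ratio with 80% and 95% confidence intervals, and a place in a forest plot, using the pooled treatment groups of the primary analysis. The only condition is at least 10 events in the subgroup, counted in total over the groups. The same section adds: "Safety analysis (i.e. AE) will be conducted based on age subgroup, and ideal body weight normalized dose quartiles".

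Section 6.1.4 gives the definitions: "Total body weight normalized dose=Activity in the first dose administered to subject /body weight used for first dose" and "Ideal body weight normalized dose= Activity in the first dose administered to subject /ideal body weight". Activities given under the updated NIST standard are divided by 1.1, so exposure is on the 50 or 80 kBq/kg scale throughout.

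The assigned doses are in Section 1:
- "Arm A: 6 doses of 50 kBq/kg (55 kBq/kg after implementation of NIST update) radium-223 dichloride every 4 weeks"
- "Arm B: 6 doses of 80 kBq/kg (88 kBq/kg after implementation of NIST update) radium-223 dichloride every 4 weeks"
- "Arm C: 12 doses of 50 kBq/kg (55 kBq/kg after implementation of NIST update) radium-223 dichloride every 4 weeks"

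Section 6.6 does not state whether the quartile cut points come from all subjects or are set separately within each dose level.

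**The concern.** A subgroup variable for a treatment comparison should not contain the treatment. Here it does. Activity is prescribed per kg, so activity divided by dosing weight returns the randomised dose level. Quartiles of that quantity over all subjects largely re-create the arms, and a hazard ratio of high against standard dose inside a one-arm quartile does not exist.

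The ideal-weight version multiplies the assigned dose by the total-to-ideal weight ratio. Where the arms overlap on it, relatively heavy standard-dose men meet relatively light high-dose men.

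At stake is part of a stated exploratory objective, the effect of body size on efficacy and safety (Section 2). Forest-plot rows would be empty or hard to interpret, and the adverse-event tables would not separate body size from dose. The primary analysis is not touched.

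**Working it through.** **Inputs from the SAP.** 360 subjects randomised 1:1:1, Arms A and C pooled for Comparison 1 (240 versus 120), hazard ratio 0.667, 186.61 expected events, one-sided 0.10, power 90.5% (Section 3.4); doses of 50, 50 and 80 kBq/kg (Section 1); the normalized-dose definitions (Section 6.1.4).

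**Assumptions, not in the SAP.** Coefficient of variation (CV) of delivered dose around assigned dose, 2–15%; CV of the total-to-ideal weight ratio (TBW/IBW), 10–25%.

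**1. The plan's own figure.** Power = Φ(√(D·p(1−p))·|ln HR| − z₀.₉₀) with D = 186.61 and p = 1/3. √(186.61 × 2/9) = 6.440; 6.440 × 0.405 = 2.608; 2.608 − 1.282 = 1.326; Φ = 0.908. This agrees with the stated 90.5%. A simulation of the stated design gave 189.2 events, 68.5 of them in Arm B, and 90.7% power. Events per subject are then (189.2 − 68.5)/240 = 0.50 in A+C and 68.5/120 = 0.57 in B.

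**2. Total-weight version.** Normalized dose = assigned kBq/kg, apart from delivery error. Each quartile holds 360/4 = 90 subjects. Ranking 240 subjects near 50 below 120 near 80 gives, as A+C/B:

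| Quartile | No overlap | Delivery CV 10% | Delivery CV 15% |
|---|---|---|---|
| 1 | 90/0 | 90.0/0.0 | 89.6/0.4 |
| 2 | 90/0 | 89.9/0.1 | 88.2/1.8 |
| 3 | 60/30 | 60.1/29.9 | 61.8/28.2 |
| 4 | 0/90 | 0.0/90.0 | 0.4/89.6 |

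Only the third quartile contains both groups in useful numbers. It sets the 60 highest-dosed standard-arm subjects against the 30 lowest-dosed high-dose subjects.

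**3. Ideal-weight version.** Normalized dose = assigned kBq/kg × TBW/IBW. Simulated averages, A+C/B:

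| Quartile | CV 10% | CV 15% | CV 20% | CV 25% |
|---|---|---|---|---|
| 1 | 90.0/0.0 | 90.0/0.0 | 89.6/0.4 | 88.6/1.4 |
| 2 | 90.0/0.0 | 89.2/0.8 | 85.8/4.2 | 81.3/8.7 |
| 3 | 60.0/30.0 | 59.4/30.6 | 57.3/32.7 | 56.3/33.7 |
| 4 | 0.0/90.0 | 1.4/88.6 | 7.3/82.7 | 13.9/76.1 |

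Precision where a fit is possible: SE(log HR) ≈ √(1/events in A+C + 1/events in B). At CV 25%, the second quartile has 81.3 × 0.50 = 40.7 and 8.7 × 0.57 = 5.0 events, so SE = 0.48 and the 80% interval is the estimate times or divided by exp(1.282 × 0.48) ≈ 1.84. The fourth has 7.0 and 43.4 events, SE 0.41, factor 1.69. At CV 20% the factors are about 2.3 and 2.0. A balanced quartile with 186.61/4 = 46.7 events has SE 1/√(46.7 × 2/9) = 0.31 and factor 1.49.

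Confounding: at any one value of ideal-weight normalized dose, a standard-dose man has a TBW/IBW ratio 80/50 = 1.6 times that of a high-dose man.

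**4. The event threshold.** A one-arm quartile of 90 has about 90 × 0.50 = 45 events (A+C) or 90 × 0.57 = 51 (B). Both exceed 10 in total, so the rule does not suppress the row.

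**5. Quartiles cut within dose level.** Each would hold 240/4 = 60 and 120/4 = 30 subjects. With 46.7 events, power at hazard ratio 0.667 is Φ(3.220 × 0.405 − 1.282) = 0.51, so a hazard ratio can be estimated. Within a dose level, however, total-weight normalized dose varies only through delivery error, so those quartiles carry no information on body size.

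**The case against.** The strongest reply is that quartiles within dose group may be intended. Section 6.1.4 introduces the quartiles in a list of summaries by treatment group, and Section 6.6 refers to the pooled treatment groupings. That reading is possible but not stated. The Section 6.6 wording governs every listed subgroup and concerns the pooling of Arms A and C, not cut points. For total weight, the within-dose reading leaves only delivery error.

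The quoted line might also mean quartiles of baseline weight in kg plus quartiles of ideal-weight normalized dose. Since Section 6.1.4 defines a total-weight normalized dose for quartile summaries, this reading is less natural, and it leaves the ideal-weight problem in place.

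A reader might infer that no hazard ratio by normalized-dose quartile can be obtained, or that the body-size objective is lost. The documents do not support either:
- The third quartile is mixed in both versions, and with wide body-size spread the ideal-weight second and fourth quartiles can be fitted, though poorly.
- Comparison 2 sets Arm A against Arm C, which share the same first dose per kg.
- Section 6.2.1 (Kaplan-Meier curves and a Cox model by BMI) and Section 6.6 (BMI subgroups and Cox models) address body size without using dose, and remain valid.

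Nor do the adverse-event tables necessarily show dose level alone. Section 6.4.1 reports treatment-emergent events by arm as treated. If the quartile tables keep arm columns, the fault is near-empty cells; only if they are collapsed over arms do they mainly show dose level.

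It is also fair that these are descriptive summaries with no decision attached.

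**Conclusion.** The point stands for Comparison 1 and for the adverse-event tables by ideal-weight normalized-dose quartile. With quartiles cut over all subjects, three of the four total-weight hazard ratios cannot be estimated. This follows from the SAP's definitions and allocation and hardly depends on dosing error: at an assumed 15% CV, fewer than 2 of 90 subjects on average come from the other group. For ideal weight the result is weaker. Over an assumed TBW/IBW CV of 10–25%, the hazard ratios outside the third quartile range from absent to imprecise and confounded with body size.

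The total-weight analysis does not serve its purpose on either reading of the cut points, so stating the cut-point rule would not be enough. A lesser consequence is that randomised but untreated ITT subjects have no first-dose activity and fall in no quartile. The matter is worth correcting, but it is confined to exploratory and descriptive output.

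**What to change.** In Section 6.6, for Comparison 1 and for the adverse-event tables, replace the normalized-dose quartiles with quartiles of a baseline body-size measure that does not contain the assigned dose: the total-to-ideal body weight ratio, or baseline body weight. State that cut points are taken over all subjects. Randomisation then gives about 60/30 subjects per quartile on average.

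Cutting within dose level is an acceptable alternative for the ideal-weight version only, with a note that a quartile then covers a different dose range in each group. It should not be used for the total-weight version.

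The cost is about one line of text and the matching table and figure specifications. Height, weight and ideal body weight are already part of the planned summaries in Section 6.1.2. Comparison 2 and the BMI analyses need no change.
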